3.2 Demographic and Baseline Characteristics

- All key efficacy measurements will be summarized at baseline visit.

3.3 Medical History and MS Medical History

- Medical history will be coded using the MedDRA, version 23.1 instead of 21.1 as mentioned in SAP section 7.6.

3.4 Prior and Concomitant Medication

PRIOR AND CONCOMITANT MEDICATIONS

The definition of a prior medication is defined as any medication taken prior to the date of first treatment and either stopped prior to the first treatment or continued after it.

3.5 Missing Start and Stop Dates for Adverse Events and Concomitant Medications

The following imputation rule will be used in this study in addition to SAP mentioned in section 6.8.1

- For Start Date: If Day and Year is present but Month is missing then impute January as month.

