6.8.1. Missing Start and Stop Dates for Adverse Events and Concomitant Medications

The following imputation rule will be used in this study:

For onset or start dates as well as end or stop dates for AEs or Medications, a conservative approach will be used, where if an event can be considered as being on treatment it will be assumed to be so.

For onset or start dates for AEs or Medications, the following rules will be used to impute partial dates:

- a) If month and year are known, but the day is unknown, the day will be assumed to be the 1st, unless the treatment was started that month of the same year in which case the day will be set to the day of start of treatment.
- b) If only the year is known but both day and month are missing, the day and month will be assumed to be 1st January, unless the treatment started that year, in which case the day and month will be imputed to be the treatment start day and month.

For end or stop dates the following will be used to impute partial dates:

- a) If month and year are known, but the day is unknown, the day will be assumed to be the last day of the month, unless the date of last treatment is in the same month and year, in which case the day of last treatment will be used to impute the end or stop day.
- b) If only the year is known but both day and month are missing, the day and month will be assumed to be 31st December, unless the date of last treatment is in the same year, in which case the day and month of last treatment will be used to impute the end or stop day and month.

In addition:

If an AE start date is completely missing or it is unclear whether the event occurred prior to or in the treatment period, the AE will be assumed to be treatment emergent (after initiation of first treatment).

If a medication end date is completely missing or it is unclear whether the medication was taken prior to or in the treatment period, the medication will be assumed to be taken during the treatment period as a “concomitant medication”.

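### SAP Appendix I 3.5 imputes January for an unknown AE start month without the treatment-year exception of SAP 6.8.1, so the imputed date can contradict the event's treatment-emergent status

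*SAP*

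**What the plan says.** SAP 6.8.1 takes a conservative approach to partial dates, "where if an event can be considered as being on treatment it will be assumed to be so". It has two rules for partial start dates. With month and year known, the day is set to the 1st, "unless the treatment was started that month of the same year", and in that case the treatment start day is used. With only the year known, the date is set to 1 January, "unless the treatment started that year, in which case the day and month will be imputed to be the treatment start day and month". The section closes with a catch-all: if an AE start date is wholly missing or "it is unclear whether the event occurred prior to or in the treatment period, the AE will be assumed to be treatment emergent".

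It has no rule for a known day and year with a missing month. SAP Appendix I, section 3.5, fills that gap: "If Day and Year is present but Month is missing then impute January as month". It introduces the rule with "The following imputation rule will be used in this study in addition to SAP mentioned in section 6.8.1".

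SAP section 8 confines AEs from before first treatment to the listings. SAP 6.1 requires listings to show the partial date together with the imputed one.

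**The concern.** January is the earliest possible month. In the calendar year of first treatment it therefore pulls the onset towards the pre-treatment side, which is the opposite of what 6.8.1 sets out to do.

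Neither section says whether timing still counts as unclear once January has been filled in, or whether the TEAE flag follows the imputed date or the catch-all. Two programmers could handle the same AE differently. Safety and tolerability is the primary endpoint and the TEAE tables are its main output, so the flag should not depend on that choice.

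**Working it through.** **The three start-date rules side by side**

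| Known part of start date | Imputed value | Exception tied to start of treatment |
|---|---|---|
| Month and year (6.8.1) | 1st of the month | Yes: same month and year |
| Year only (6.8.1) | 1 January | Yes: same year |
| Day and year (Appendix I 3.5) | January | None |

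**Worked example (assumed dates).** First treatment is on 15 June 2019.
- AE on the 20th of an unknown month in 2019: Appendix I 3.5 gives 20 January 2019. By SAP 6.7.2 the study day is 20 January minus 15 June = −146. Yet the 20th falls on or after first treatment in seven months (June to December).
- AE in 2019 with day and month both unknown: 6.8.1 gives 15 June 2019, which is Study Day 1.

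Knowing more of the date gives the less conservative result.

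**How often January contradicts the principle.** The plan gives no figure to reproduce, so I enumerated the rules. These are shares per AE with this date pattern, not predicted effects.
- *By recorded date.* Every first-treatment date in 2019 against every known day 1 to 31, with the AE in the same year, gives 365 × 31 = 11,315 pairs. In 10,850 the AE could be on treatment. January dates 10,354 of these before treatment: 10,354 / 10,850 = 95.4%. For 2020 it is 10,385 / 10,881 = 95.4%. For first treatment in February to November the share is 100%.
- *By true onset.* Every first-treatment date in 2019 against every onset from day 0 to day 196 (28 weeks × 7) gives 365 × 197 = 71,905 on-treatment onsets. January alone dates 49,399 before first treatment: 49,399 / 71,905 = 68.7% (68.8% for 2020). The other 31.3% keep an on-treatment date, mostly because the onset falls in the next calendar year, where January is already after first treatment.
- *With the 6.8.1 principle and catch-all applied to the flag:* none of these onsets loses TEAE status. Only the listed date is wrong.

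**Effect on a table.** With 20 treated patients, one patient whose only event in a row is lost changes that row by 1/20 = 5.0 percentage points. The number of AEs with this pattern is not in the documents, so no expected effect can be given.

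**Check of the remedy.** The rule proposed below dates 0 of the 71,905 on-treatment onsets before first treatment. It needs the limit at the stop date. Take first treatment on 15 June, an AE on the 10th of an unknown month, and a stop date of 1 July. Every possible onset (10 January to 10 June) is before treatment. Without the limit the rule would give 10 July, after the AE had ended; with it, no on-treatment date fits and January is used. Among 14-day AEs spanning first treatment, about 95% get a start after their stop without the limit, and none with it.

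**The case against.** The strongest reply is that the text already protects the flag. Appendix I 3.5 supplements 6.8.1 and withdraws nothing from it. The principle and the catch-all both remain, and both make an AE that could be on treatment a TEAE. This stands, and it is why the point is small. It does not remove the date that contradicts the flag, and it leaves the order of precedence unstated.

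The practical safeguards also count. AEs are reviewed at every visit and telephone call (protocol Table 1), which helps place an onset. Logic and consistency checks are planned (protocol 12.2.1, SAP 6.3). The listings keep the partial date visible.

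Three stronger readings are tempting, and the documents do not support them:
- *That Appendix I 4.1 excludes these AEs because it refers to onset date.* It counts every AE with onset after first treatment whatever its severity. That widens inclusion; it does not say that only those AEs qualify, and it does not cancel the catch-all.
- *That on-treatment medication use is lost, since the heading of 3.5 covers medications too.* Appendix I 3.4 defines a prior medication as "any medication taken prior to the date of first treatment and either stopped prior to the first treatment or continued after it", and protocol 6.2 defines concomitant medication by use during or after the first transplantation. A drug given a January start that continued on treatment still meets the concomitant definition. Where timing is unclear, 6.8.1 adds that "the medication will be assumed to be taken during the treatment period".
- *That misdated AEs can be sorted into plausible and obviously wrong by whether the date precedes consent.* The protocol gives the 10-week pre-treatment period as approximate and allows flexible windows for the manufacturing-driven visits, so there is no firm cut-off.

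**Conclusion.** The omission is a fact of the text: the added rule lacks the treatment-year exception that both partial start-date rules of 6.8.1 carry, and in the year of first treatment it can give a date that conflicts with the section's own principle. On the better reading the AE is still tabulated as a TEAE, and the defect is a listed date and study day that disagree with the flag. A reader might infer that AEs will certainly drop out of the TEAE tables; that happens only if a programmer lets the imputed month settle the timing.

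This is a minor point. The shares above assume first-treatment dates spread evenly over the year and onsets spread evenly over 28 weeks, and they apply only to AEs with this unusual date pattern, of which there may be none.

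**What to change.** In Appendix I 3.5, for AEs only: when only the start month is missing and treatment started in that year, impute the earliest date that fits the known day and year, is on or after first treatment, and is not later than any known stop date. Use January only if no such date exists.

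Add that the principle and catch-all of 6.8.1 govern TEAE status whatever date is imputed, except where the known day, year and stop date leave only pre-treatment onsets.

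The cost is two or three sentences and minor programming. The downside is that some truly pre-treatment AEs with this pattern will be counted as TEAEs. With no known stop date and onsets spread evenly before first treatment, the share is 21,901 / 25,550 = 85.7% for a 10-week pre-treatment period and 13,668 / 15,330 = 89.2% for a 6-week one; the January date alone would count none. Section 6.8.1 already accepts error in this direction, and its principle would make the same AEs treatment emergent.

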3.6 Study Drug Exposure and Compliance

• Additional analysis

1. Descriptive statistics summary for duration between treatments 1-2, 2-3 and 1-3.
2. Summary of number and % of subjects with durations between treatments 1-2 and 2-3 for below categories.
 - a. ≤ 30 days before 8 weeks
 - b. >30 and ≤ 15 days before 8 weeks
 - c. >15 and <5 days before 8 weeks
 - d. Within 5 days of 8 weeks
 - e. >5 and ≤ 15 days after 8 weeks
 - f. >15 and ≤ 30 days after 8 weeks
 - g. >30 days after 8 weeks
3. Summary of number and % of subjects who received first, not second study drug and second, not third study drug will be summarized.
4. Since the study drug is administered in the clinic and only three times no formal definition of compliance will be used. The number of IT administrations is summarized.

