2. INVESTIGATIONAL PLAN

2.1. OVERALL STUDY DESIGN AND PLAN

This will be the fifth clinical study conducted by Brainstorm Cell Therapeutics to study autologous NurOwn® (MSC-NTF cells) in a neurodegenerative disease.

The first three completed studies (two open label and one placebo-controlled study) in ALS patients demonstrated the safety of a single dose of NurOwn® administered either intramuscularly or intrathecally or by combined IM and IT administration.

The ongoing Phase 3 double blind placebo-controlled study for 200 ALS patients (randomized 1:1) will evaluate the safety and efficacy of three repeat transplantations, 2 months apart.

This is a proof-of-concept Phase 2 open label study that will be conducted in 20 participants with progressive MS with EDSS 3.0-6.5 at the Screening Visit, at multiple study sites. After providing informed consent and signing a written informed consent document all participants will be observed for a total of 9-10 months (38 weeks).

During the up to 10-week pretreatment period patients will be screened and eligibility determined. Approximately 1-4 weeks after the screening visit, bone marrow will be harvested and transferred to the cell manufacturing facility for the isolation and cryopreservation of autologous MSCs. Prior to each treatment, MSC will be thawed, cultured and induced to differentiate into MSC-NTF cells. A dose of $\sim 125 \times 10^6$ MSC-NTF cells will be administered at each treatment. At the time of consent, participants will be informed that they may not receive the transplant in case their autologous bone marrow fails to grow and reach the adequate numbers of MSC and/or MSC-NTF cells. The autologous manufacturing process is on a per-subject basis and begins upon fresh bone marrow aspirate arrival to the cleanroom facility and is completed once the cells are ready for transplantation.

The first transplantation visit (T1) will occur approximately 6 weeks after the bone marrow aspiration visit (6-10 weeks after screening/enrollment). The subsequent transplantation visits (T2 and T3, at visits 4 and 5) will follow interspaced by approximately 8 weeks (± 14 days) each (Figure 1). The patients will then be followed for 12 additional weeks after the last transplant visit (T3) at two additional visits, approximately 6 weeks apart.

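### The early dosing-interval rows in SAP Appendix I 3.6 are impossible, overlapping or incomplete as printed; a signed deviation would repair one descriptive table

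*SAP*

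**What the plan says.** SAP Appendix I, 3.6 (Study Drug Exposure and Compliance), item 2, asks for the number and percentage of participants in seven categories, lettered a to g, applied to the 1-2 and 2-3 treatment intervals.

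The late side is clear. Row g holds doses over 30 days late, row f those from 16 to 30 days late, and row e those from 6 to 15 days late, its printed form being ">5 and ≤ 15 days after 8 weeks". The central row, d, takes deviations of up to 5 days in either direction.

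The early side is where the trouble lies. The row next to the centre, c, is given as ">15 and <5 days before 8 weeks". Moving outwards, row b is given as ">30 and ≤ 15 days before 8 weeks". The outermost early row, a, is given as "≤ 30 days before 8 weeks".

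No formula for the deviation is given, and no cut-off carries a sign. Item 1 of the same section plans descriptive statistics for intervals 1-2, 2-3 and 1-3. Item 3 counts participants who missed the second or third dose. Item 4 drops a formal compliance definition and keeps the number of administrations.

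On timing, Protocol 2.1 has the second and third treatments "interspaced by approximately 8 weeks", with a tolerance of 14 days either way on each interval, and SAP 4.1 repeats this. Protocol 4.7.5 instead times the third treatment at 16 weeks ±14 days from the first. Protocol section 4 and footnote 12 of Protocol Table 1 allow a more flexible window for manufacturing reasons.

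**The concern.** The late rows (e, f, g) are well formed; the early rows are not. If a is coded as worded, it takes every dose from 1 to 30 days early, b and c are always zero, and a very early dose appears nowhere. Percentages could then sum to more than 100% (doses counted in both a and d) or less (doses in no row).

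The table matters because the documents expect doses to move: the windows may flex with manufacturing slots, and Protocol 8.3 allows treatment to be withheld for manufacturing or scheduling reasons. This is the only planned display that sorts intervals into bands by their distance from 8 weeks. What is at stake is whether those banded counts are right.

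**Working it through.** **Inputs.** Row limits: SAP Appendix I, 3.6. Window of 8 weeks ±14 days per interval: Protocol 2.1 and SAP 4.1. Third dose at 16 weeks ±14 days from the first: Protocol 4.7.5. The plan gives no figure of its own to reproduce.

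**Definition.** Deviation d = interval in days − 56, since 8 × 7 = 56. The window is 56 − 14 = 42 to 56 + 14 = 70 days, so −14 ≤ d ≤ +14. Every whole-day deviation from −55 to +56 (112 values) was assigned to rows a to g under two readings.

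**Reading 1, literal.** Days before is a positive count, x = 56 − interval.

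- Row b needs x > 30 and x ≤ 15: no solution.
- Row c needs x > 15 and x < 5: no solution.
- Row a takes x = 1 to 30, intervals of 26 to 55 days. Of these 30 values, 14 are within 14 days (x = 1 to 14, intervals 42 to 55) and 16 are beyond it (x = 15 to 30, intervals 26 to 41).
- Rows a and d both take x = 1 to 5, intervals of 51 to 55 days.
- x > 30, intervals of 25 days or less, has no row. That is 25 of the 112 values checked (d = −55 to −31).

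**Reading 2, signed.** The early limits are treated as negative deviations.

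| Row | d | Relative to ±14 days |
|---|---|---|
| a | −30 or earlier | all outside |
| b | −29 to −15 | all outside |
| c | −14 to −6 | all inside |
| d | −5 to +5 | all inside |
| e | +6 to +15 | 9 values inside, 1 outside (+15) |
| f | +16 to +30 | all outside |
| g | +31 or later | all outside |

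All 112 values fall in exactly one row. Rows a + b are exactly the doses more than 14 days early. Rows f + g miss only doses exactly 15 days late. The outer limits are also slightly uneven: −30 sits in the outermost early row, while +30 does not sit in the outermost late row.

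**Third dose.** Under Protocol 4.7.5, with dose 2 at day 42 to 70 and dose 3 at day 98 to 126 (112 ± 14):

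- shortest 2-3 interval with both visits in window: 98 − 70 = 28 days (d = −28);
- longest: 126 − 42 = 84 days (d = +28).

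Under Protocol 2.1, two successive 70-day intervals are each allowed, but 70 + 70 = 140 days, which is 14 days past the 126-day limit in 4.7.5. A dose can therefore be in window under one section and out of window under the other.

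**The case against.** The strongest reply is that this is a notation slip. Read as signed deviations, the rows mirror the late side and leave no gap, and a programmer meeting two impossible rows would probably code them that way. That stands as the likely intent. It does not rescue the text, which says days before, shows no sign and defines no deviation.

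A reader might also infer more than the documents support:

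- **That this is the only planned summary of adherence to the schedule, so the report could not say who received three doses.** It is not. Items 1, 3 and 4 of the same section, SAP 7.8 (administrations received, first-to-third duration), SAP 7.1 (discontinuation by number of treatments) and SAP 7.3 (important deviations) cover doses received and interval length. None is specified to count intervals by timing band.
- **That early doses will be misclassified and out-of-window doses cannot be counted.** This holds only if the rows are coded literally. On the signed reading the early count is exact, and the late count is wrong only for doses at exactly +15 days.
- **That up to 40 intervals are affected.** 20 × 2 = 40 is the maximum number of intervals in the study. On the literal reading only early intervals are disturbed.

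It is also fair to say that the section never states that the table is meant to count out-of-window doses, so aligning the rows with 14 days is a sensible improvement rather than the correction of a broken promise.

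**Conclusion.** The point holds as a wording error in an analysis rule. As printed, two of the seven rows are empty by construction, one overlaps its neighbour for doses 1 to 5 days early and pools doses on both sides of the 14-day limit, and doses more than 30 days early have no row. On the probable signed reading, the mismatch with the ±14-day window shrinks to the single day +15.

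The consequence is limited to counts in one descriptive exposure table. No endpoint, analysis population or test depends on it. How many participants would be miscounted cannot be stated, because the documents give no observed intervals. The in-window and out-of-window labels used here assume ±14 days per interval, as in Protocol 2.1; for the third dose Protocol 4.7.5 gives a different reference point. Severity: minor.

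**What to change.** In SAP Appendix I, 3.6, define deviation = (date of dose k+1 − date of dose k) − 56 days. For intervals 1-2 and 2-3, print exclusive rows: < −30; −30 to −15; −14 to −6; −5 to +5; +6 to +14; +15 to +30; > +30. These cover every whole day once, are symmetric, and break at 14 days on both sides.

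Tabulate the 1-3 deviation from 112 days as well, since Protocol 4.7.5 times the third dose from the first.

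Do not label any row in window for the third dose until Protocol 2.1 and SAP 4.1 (±14 days for each interval) have been reconciled with Protocol 4.7.5 (16 weeks ±14 days from the first dose). An in-window row of −14 to +14 on the 2-3 interval would mark some third doses as late or early although 4.7.5 allows them. Which statement governs is for the sponsor to settle.

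The cost is a few lines of Appendix text and the reprogramming of one table, plus the reconciliation of the two window statements.

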4. SAFETY ANALYSES

4.1 Adverse Event

- Adverse Event will be coded using the MedDRA, version 23.1 instead of 21.1 as mentioned in SAP section 8.
- Summary for MS relapse will not be done separately in table/listing due to lack of data.
- As mentioned in section 8 of SAP, Treatment-emergent adverse event (TEAE) is an AE that occurs for the first time after initiation of first treatment or if it had occurred prior to initiation first treatment, it worsens in severity after initiation of first treatment. In current TEAE analysis all AEs with onset date after initiation of first treatment are considered as TEAEs irrespective of severity.

- The AE eCRF page assesses discontinuation from treatment (and not from study) while the End of Study (EoS) eCRF page assesses if a subject was discontinued from the study, hence there may be differences between what is recorded on these eCRF pages.. The disposition Table will display the number of subjects discontinued from study as recorded on the end of study page. No AE Tables will be generated for AEs leading to study discontinuation as this data was not collected in the AE eCRF. A listing will provide AE's from the AE datasets for subjects who discontinued the study based on an AE as recorded in the end of study page
- Certain tables will not be generated since there are too few subjects (example procedure related adverse events etc.). But subjects with these AE criteria's will be summarized in listings.

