7. SAFETY REPORTING

For this study, AEs and SAEs will be collected from the time of informed consent at the screening visit through the last study visit (Visit 7 or an Early Termination visit) as detailed in Sections 4.6.-4.8.

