9.3.5. Safety analyses

All safety analyses will be based upon the Safety Population.

All AEs will be coded to System Organ Class (SOC) and Preferred Term (PT) using the Medical Dictionary for Regulatory Activities (MedDRA®). The number of treatment-emergent adverse events (TEAEs) and the number of participants with any TEAEs (along with percentages) will be tabulated by SOC and PT.

A TEAE is an AE that occurs for the first time after initiation of treatment or if it had occurred prior to treatment, worsens in severity after initiation of treatment.

Separate summaries will be provided for the following categories of AEs:

- TEAEs
- TEAEs by severity
- Treatment-related TEAEs
- Serious TEAEs

When evaluating changes in safety parameters, Baseline will be defined as the last measurement prior to first transplantation (i.e., prior to initiation of treatment).

Abnormalities in hematology, blood chemistry and ECG assessments will be summarized.

MRI (T1 and T2 weighted images) will be assessed for study safety at baseline and at the end of the study.

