8. SAFETY AND TOLERABILITY

All safety analyses will be based upon the Safety Population.

All AEs will be coded to SOC and PT using the MedDRA, version 21.1.

A Treatment-emergent adverse event (TEAE), referred to subsequently as just TEAE or AE is an AE that occurs for the first time after initiation of first treatment or if it had occurred prior to initiation first treatment, it worsens in severity after initiation of first treatment.

AE's that occur prior to initiation of first treatment will only be in the listings and not included in any summary Tables.

AE's related to the Bone Marrow Aspiration will be included in a separate listing.

When evaluating changes in continuous safety parameters (such as laboratory measurements, vital signs, ECGs, etc.) , Baseline will be defined as the last measurement prior to first transplantation (i.e., prior to initiation of treatment).

Additional details for analysis of safety data are detailed below.

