8.1. Overall Summary of Tolerability

The overall summary of tolerability table will present data by the NurOwn® group. Entries in this table will include:

1. Number of TEAEs
2. Subjects with at least one
 - a. Adverse event including procedure related AEs
 - b. Procedure related AEs
 - c. AE excluding procedure related AEs
 - d. AE related to the study medication
 - e. Severe AEs including procedure related Severe AEs
 - f. Severe AEs related to procedure
 - g. Severe AEs excluding procedure related Severe AEs
 - h. Severe treatment related AEs
 - i. Serious AEs
 - j. Serious treatment related AEs
 - k. AEs leading to study discontinuation
 - l. MS relapses
 - m. AEs leading to death

The above summaries will include the number of events as well as number and percentage of subjects experiencing at least one TEAE.

The subject data listing provides a complete list of all AEs as recorded in the CRF and supports this table and all other AE summary table subsets.

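### SAP Appendix I applies a TEAE rule based on onset date alone, so a pre-treatment AE that worsens after dosing may be missing from the TEAE tables

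*SAP*

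**What the plan says.** Protocol 9.3.5 defines a TEAE in two limbs: an AE that first occurs after treatment starts, "or if it had occurred prior to treatment, worsens in severity after initiation of treatment". SAP section 8 uses the same two limbs; under the second, an earlier AE counts if "it worsens in severity after initiation of first treatment". SAP section 8 then adds a placement rule: "AE's that occur prior to initiation of first treatment will only be in the listings and not included in any summary Tables".

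SAP Appendix I, section 4.1, cites SAP section 8 and repeats its definition, including the second limb ("if it had occurred prior to initiation first treatment, it worsens in severity after initiation of first treatment"). The next sentence gives the rule for the analysis: "In current TEAE analysis all AEs with onset date after initiation of first treatment are considered as TEAEs irrespective of severity".

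Two other provisions matter. Protocol section 7 sets the collection window: "AEs and SAEs will be collected from the time of informed consent at the screening visit through the last study visit". SAP 8.1 sets the coverage of the listings: "The subject data listing provides a complete list of all AEs as recorded in the CRF".

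**The concern.** Safety and tolerability form the primary endpoint, and the TEAE flag decides which events enter the AE summary tables. AEs are collected from consent, over a pre-treatment period of up to 10 weeks that includes the bone marrow aspiration. Some AEs may therefore already be open when the first dose is given. The worsening limb exists to catch such an event if it becomes more severe after dosing.

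The Appendix I rule has no place for that event. It asks only when the AE began, and it sets severity aside, although the second limb needs a severity comparison. The study has no control arm against which an undercount might show. Appendix I also removes some summaries that might have shown the same signal: there is no separate MS relapse summary, and certain tables, such as those for procedure-related AEs, are replaced by listings.

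**Working it through.** The documents give no figure for this point, so the check compares the rules case by case.

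**Inputs.** Two-limb definition: Protocol 9.3.5 and SAP section 8. Onset-date rule: SAP Appendix I 4.1. Placement of pre-treatment AEs: SAP section 8. Percentage denominator: the Safety Population (SAP 8.2), planned at 20.

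**Case by case**

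1. The AE first occurs after the first dose. Both rules count it.
2. The AE occurred before the first dose and recurs later, no worse, as a new record. The two-limb definition does not count it; Appendix I does. Here Appendix I is broader.
3. The AE began before the first dose and never worsens. Neither rule counts it, and it goes to the listings.
4. The AE began before the first dose and worsens later, and the worsening is a **new record** with its own onset date. Both rules count it.
5. The AE began before the first dose and worsens later, and the worsening is a severity change on the **original record**. The two-limb definition counts it. The Appendix I rule does not, because the onset date precedes treatment. SAP section 8 then keeps it in the listings.

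Only case 5 is an undercount, and what separates it from case 4 is the recording convention. Protocol 7.1.5 asks the investigator to follow an AE once recorded, and to update the AE page when an SAE resolves. That leans towards one continuing record, but it gives no rule for a change in severity.

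**Scale.** One participant in a row is 1/20 = 5.0 percentage points. With exact (Clopper-Pearson) 95% intervals:

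- 1/20 = 5.0%. Lower limit 1 − 0.975^(1/20) = 0.1%; upper limit 24.9%.
- 0/20 = 0%. Upper limit 1 − 0.025^(1/20) = 16.8%.

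So a row holding one missed worsening and no other event would read 0% (0 to 16.8%) where the protocol definition gives 5.0% (0.1 to 24.9%).

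The full 5 points are lost only if the participant has no other event in that row. A participant with another event there stays in the row, but the severity tables report each participant at maximum severity (SAP 8.2.1), so the severity shown may be too low.

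**The case against.** The best defence is that the Appendix I sentence adds events and removes none. It follows a full restatement of the two limbs, it does not say that only later-onset events count, and its reference to severity can be read as a conservative step that brings in recurrences no worse than before. Where Appendix I replaces SAP text, it usually says so, as it does for the MedDRA version and the uric acid unit. On this reading the worsening limb survives.

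This has force: the limb is not expressly deleted. But the sentence is offered as the rule for the analysis actually being done, and it contains no severity comparison. A programmer who follows it would not flag case 5. A text that supports two derivations of the main safety variable still needs correcting. The onset-only reading also sits badly with SAP 6.8.1, which treats AEs of unclear timing as treatment-emergent.

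The other objections stand, and they set the limits of the point:

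- The loss depends on a recording convention that the documents do not give.
- Read after the two-limb definition, the listings-only sentence in SAP section 8 most naturally covers pre-treatment AEs that are not TEAEs. The difficulty arises when it is combined with the Appendix I rule.
- Only AEs that begin between consent and first treatment are exposed. Conditions present at entry are recorded as medical history (SAP 7.6).
- Participants whose cells fail to grow may never be treated, so the Safety Population could be smaller than 20, which would make each participant's share slightly larger than 5 points.

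A reader might infer that a worsened pre-existing AE disappears from every safety table. The documents do not support that. Laboratory, vital-sign and MRI summaries do not use the TEAE rule. The event stays in the all-AE listing, though without a treatment-emergent flag, and in the serious, severe or related listings where it qualifies.

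**Conclusion.** The point holds in a conditional form. The operational rule in Appendix I 4.1 departs from the definition in Protocol 9.3.5 and SAP section 8, which it has just restated, by leaving out the worsening test. Where a worsening is kept on the original record, the event would be missing from the TEAE summary tables and visible only in listings.

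For this class of event the error can only be an undercount. The net effect on total TEAE counts is unknown, because the same rule also brings in recurrences that are no worse than before. The number of affected participants cannot be found from the documents and may be zero. The figure of 5 percentage points per participant assumes a denominator of 20 and no other event for that participant in the row.

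This is more than missing detail, because the stated rule and the protocol definition give different answers for the primary endpoint.

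**What to change.** 1. Amend the Appendix I 4.1 sentence so that a TEAE is either (a) any AE that starts after the first treatment has been initiated, whatever its severity, which keeps the broader inclusion of recurrences; or (b) any AE that started earlier and increases in severity after the first treatment has been initiated. If the eCRF keeps the original onset date, flag (b) by the date of worsening.
2. State the eCRF convention: whether a worsening opens a new AE record or updates the existing one.
3. Make clear that the listings-only sentence in SAP section 8 applies only to pre-treatment AEs that do not worsen.

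The cost is a short text change and one derivation flag. TEAE counts may rise slightly. If worsenings were always entered as new records, the tables will not change, and the text will then show why.
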